We have previously demonstrated the effectiveness of a stepped-care intervention in the Can-Sleep program for individuals with significant sleep disturbance who have received cancer treatment. Can-Sleep involves a self-directed therapeutic intervention using a self-help booklet (step 1), followed up with a CBT group for those still experiencing clinical levels of sleep disturbance (step 2). Approximately 53% of participants required step 2/CBT-Group. The purpose of the current project is to design an Australian-first, evidence-informed stepped-care CBT intervention for cancer survivors targeting fatigue, and test its feasibility.

AIMS

The overall aim of the project is to evaluate the feasibility of a stepped-care intervention that identifies and treats CRF in adults who have completed treatment for cancer.

Specific project aims:

1. To assess the feasibility and acceptability of a novel stepped-care approach to managing cancer-related fatigue.
 - a. Feasibility (e.g., adherence, recruitment and retention rate)
 - b. Acceptability (e.g., usefulness of booklet and phone calls/emails, ease of use of booklet, time spent reading booklet)
 - c. Satisfaction (e.g., perceived satisfaction with the amount of support received, extent to which program has met needs)
 - d. Proportion of people being referred to ‘STEP 2’
2. Assessment of processes, procedures and costs associated with implementing REFRESH in a clinical setting.
3. To explore whether participation in the stepped-care intervention shows promise for treatment response: improvements in fatigue, quality of life and emotional wellbeing.

PROJECT DESIGN

This project will evaluate the ‘REFRESH’ Program that aims to address problems with persistent fatigue amongst cancer survivors. Available funding is insufficient to achieve

REFRESH: Finding New Energy after Cancer

[figure not shown]
adequate power to evaluate effectiveness of the program on CRF, therefore a non-randomised design with before and after measures will be used.

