- Participants will be asked for their feedback on each Chapter of the self-management booklet as they are working through STEP 1. There are approximately 5 brief questions at the end of each chapter in the booklet. These feedback questions can be removed from the booklet and sent to the research team via email or mail by participants (see TIME 1 Questionnaire PART A (T1Q-A) in Appendix A.3).
- At the completion of the week 5 phone call, participants will be emailed a link to PART B of the TIME 1 online questionnaire (or a paper copy if preferred) (T1Q-B) (see Appendix A.4).
- The FACIT-F score from the T1Q-B will determine eligibility for STEP 2. Participants with a FACIT-F score of 10 or more points higher than baseline will finish their CBT Fatigue treatment, unless they score below 34 (severe). This was established a clinically important improvement (Reddy, Bruera, Pace, Zhang, & Reyes-Gibby, 2007).
- Participants with a FACIT-F score on the T1Q-B questionnaire of less than 10 points higher than baseline and/or below 34 will be offered STEP 2. The decision to be 'stepped up' to STEP 2 will also be made in conjunction with the psychologist's clinical judgement/interview at the week 5 phone-call of STEP 1 (e.g., if questionnaire measures don't appear congruent with clinical observations of further support needs).
- Participants who do not go on to STEP 2 of the program will complete Time 2 Part B Questionnaires (T2Q-B) (see below) 6 weeks after completing the self-management booklet, with the exception of the feasibility, acceptability and satisfaction measures (which will not be applicable as they will have not completed STEP 2).

Recruitment to STEP 2: Administration of Individual CBT

[figure not shown]
- Participants eligible for STEP 2 will be offered up to 4 CBT sessions with a clinical psychologist. These sessions can be delivered one-on-one or in a small group and via face to face or via Telehealth modalities. For Telehealth sessions a secure allied health telehealth platform called CoViu (recommended by the Australian Psychology Association) or the Peter Mac telehealth platform will be utilised.

Administration of TIME 2 Questionnaires (following STEP 2)

- After the participant's last CBT session, PART A of the TIME 2 Questionnaire (T2Q-A) will be administered (either in person or via Telehealth) (Appendix A.5).

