Changes from baseline at follow-up assessments for fatigue (FACIT-F), self-efficacy (PSEFSM) and Quality of Life (Ed-5D-5L) will be analysed descriptively (means and standard deviations). This will be done separately for patients who participate in Step 1 only and for those who participate in Steps 1 and 2. Effect size estimates (i.e. standardised measures of change from baseline; in this case, mean change divided by the baseline standard deviation), as described by Kazis and colleagues, will be used to characterise the size of observed differences (Kazis, Anderson, & Meenen, 1989)

Free text items from participant questionnaires will be summarised using content analysis, whereby the content of free responses will be coded and grouped, where applicable. It is worth noting that free text items mostly accompany pre-determined response options, so it is not envisaged that all participants will opt to respond to free text items.

ETHICAL CONSIDERATIONS

This project will be conducted according to the NHMRC national Statement on Ethical Conduct in Human Research (2007 and updates) and the World Medical Association of Helsinki (2013 and updates).

Informed Consent

To ensure that participants do not feel obligated to participate, the study team will ensure invitees that participation is voluntary and that they may stop their involvement in the project at any time. The study team will explain that their decision will not impact on their care or their relationships with hospital staff.

REFRESH: Finding New Energy after Cancer

Data storage and privacy issues

A unique study identification number system will be used for all data collection for this project. This system will employ the use of paired tracking numbers, so identifiable participant information (e.g., name, date of birth) and participant contact details (e.g., email and phone number) is kept separate from questionnaire responses. Therefore, participant's personal details cannot be linked with their research involvement and questionnaire responses unless you have access to the paired tracking numbers, which will be stored in an electronic password protected excel spreadsheet that is only accessible by the research team.

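### Change from baseline is summarised only within step groups formed mainly on the Time 1 FACIT-F score, so the Step 1-only effect size is inflated and the whole program asked about in Aim 3 has no estimate

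*Protocol*

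**What the plan says.** Aim 3 is "To explore whether participation in the stepped-care intervention shows promise for treatment response" in fatigue, quality of life and emotional wellbeing. It concerns the program, not either step.

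The Data Analysis section describes changes from baseline in FACIT-F, PSEFSM and EQ-5D-5L by means and standard deviations, and adds: "This will be done separately for patients who participate in Step 1 only and for those who participate in Steps 1 and 2". The effect size is "mean change divided by the baseline standard deviation". The text does not say whether that SD is the group's own or the cohort's. It states no change summary for all participants.

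The section on the Time 1 questionnaires forms the groups: "The FACIT-F score from the T1Q-B will determine eligibility for STEP 2". Treatment ends for those with a "FACIT-F score of 10 or more points higher than baseline will finish their CBT Fatigue treatment, unless they score below 34". Those with a gain of "less than 10 points higher than baseline and/or below 34 will be offered STEP 2". The decision also draws on the psychologist's "clinical judgement/interview at the week 5 phone-call of STEP 1". Participants struggling at week 2 may enter STEP 2 before T1.

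Under Intervention Impacts, the FACIT-F change treated as clinically significant is also 10 points. The Evaluation section says the outcomes are exploratory, not powered for effectiveness, and meant as preliminary data for a future effectiveness study.

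**The concern.** The variable that assigns participants to the two tables is the variable the tables summarise. At T1 the Step 1-only group consists largely of people selected for a large gain, and the other group largely of people selected for the lack of one. Part of any such difference is measurement noise and ordinary fluctuation. That part fades by T2, downward in one group and upward in the other.

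Two misreadings follow. The Step 1-only effect size looks like strong evidence for the booklet, and the T1-to-T2 movement in the other group looks like a contribution from STEP 2. Either could be carried into the planning of the next study. The one group not selected on response, everyone enrolled, is the group Aim 3 asks about and the group left unsummarised.

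**Working it through.** **The plan's own figure.** The protocol expects about half of 50 to reach STEP 2: 50 × 0.50 = 25. Using the 53% from its earlier sleep program gives 50 × 0.53 = 26.5. This is the only figure in the document that bears on group sizes. It gives no FACIT-F SD, no baseline mean for this population and no retest correlation.

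**Assumed inputs (not in the document).** Baseline mean 28, SD 9, and the same correlation r = 0.5, 0.6 or 0.7 between any two of baseline, T1 and T2. Scores are rounded and limited to 0–52. A uniform true gain is reached by T1 and kept to T2. STEP 2 has exactly no effect. There are 1,000,000 simulated participants per scenario.

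**Rule applied.** Step 1 only if T1 − baseline ≥ 10 and T1 ≥ 34; everyone else is in Steps 1 and 2.

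**True gain 12** (48% go to STEP 2, or 24 of 50, close to the protocol's 25):

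| r | Step 1 only, T1 → T2 | Steps 1 and 2, T1 → T2 | Apparent rise | Whole cohort, T1 and T2 |
|---|---|---|---|---|
| 0.5 | +17.7 → +14.2 | +5.1 → +8.8 | 3.7 | +11.6 |
| 0.6 | +16.9 → +14.0 | +5.9 → +9.1 | 3.2 | +11.6 |
| 0.7 | +16.1 → +13.6 | +6.8 → +9.5 | 2.7 | +11.6 |

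The whole cohort falls slightly short of 12 because of the ceiling at 52. Consistency check at r = 0.6: 0.518 × 16.94 + 0.482 × 5.93 = 11.63.

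**True gain 0, r = 0.6.** Step 1 only (about 7%, or 3 of 50) shows +13.9 at T1 and +5.6 at T2. Steps 1 and 2 shows −1.0 and then −0.4. The whole cohort shows 0. Over r = 0.5 to 0.7 the Steps 1 and 2 rise is 0.8 to 0.4 points.

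**Effect size in Step 1 only at T1, r = 0.6:**

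| True gain | Divided by own-group baseline SD | Divided by whole-cohort baseline SD | Whole-cohort effect size |
|---|---|---|---|
| 0 | 2.5 | 1.6 | 0.0 |
| 10 | 2.4 | 1.8 | 1.1 |
| 12 | 2.5 | 1.9 | 1.3 |

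With the group's own SD the figure barely moves while the truth goes from nothing to 12 points.

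**Analytic check.** If selection were on change alone and nothing truly changed, E[T2 − B | T1 − B = D] = D × (1 − r) / (2(1 − r)) = D/2, so half the selected gain would vanish by T2. The simulated fall is somewhat larger (13.9 to 5.6) because the rule also requires T1 ≥ 34.

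**Other assumptions.** With mean 24 or 28, SD 10, r 0.5 to 0.8 and true gain 12, Step 1 only shows +15.8 to +19.3 at T1 and falls 2.3 to 4.9. Steps 1 and 2 rises by 1.8 to 3.6. The direction does not change.

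**Dilution.** With mean 28, SD 10, r = 0.65 and 10% fast-tracked, let 0%, 20% or 40% of those offered STEP 2 decline and count as Step 1 only. The Step 1-only T1 gain is then +14.5, +2.9 or +1.2 with no true change. With a true gain of 10 it is +16.8, +13.9 or +12.2, against +9.7 in the cohort.

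**The case against.** The protocol openly chooses an uncontrolled before-after design, disclaims effectiveness inference, plans no test and does not compare the steps. This limits the harm to misleading descriptive figures. It does not remove it: low power concerns precision, whereas selection on the outcome is a bias at any sample size, and the figures are meant as preliminary data for a later study.

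Group membership means participation, not the score rule alone. Clinical judgement, fast-tracking and refusal can put people with little gain into Step 1 only. This stands, and the dilution figures show it can matter a great deal when nothing truly changes. A reader might infer that a Step 1-only gain of 10 or more is guaranteed. That holds only for T1 FACIT-F among participants placed by the score rule. PSEFSM and EQ-5D-5L are affected only through their correlation with FACIT-F.

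A reader might also infer that an ineffective STEP 2 would be made to look effective. The document does not support that for the measure it plans. Change from baseline in Steps 1 and 2 stays slightly negative when nothing changes. With a true 12-point gain its T2 value, about +9, lies below the cohort's +11.6. The apparent rise is a T1-to-T2 contrast that the Data Analysis section does not name. It reaches 2.7 to 3.7 points only alongside a large true gain, well under the 10-point threshold.

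Finally, the cohort mean can be recovered as the weighted average of the two group means if counts are reported at each time. That makes the repair cheap; it does not make the planned summary answer Aim 3.

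**Conclusion.** The point holds in this form: the only planned change summaries are for groups selected mainly on T1 FACIT-F response, and the program-level estimate that Aim 3 needs is not stated. For those placed by the score rule, the Step 1-only T1 mean is inflated (about +16 to +18 against +11.6 in the cohort when the true gain is 12). Its effect size on its own baseline SD is about 2.4 to 2.5 whether the true gain is 0, 10 or 12. The sizes rest on an assumed mean, SD, correlation and uniform gain, and on few departures from the score rule; the direction is the same over the ranges tried. Because the aim is exploratory and the analysis descriptive, this should be fixed, but it does not invalidate the study.

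**What to change.** Amend the Data Analysis section in three respects.

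1. Make the Aim 3 summary the mean change and effect size in all enrolled participants with data, at T1 (after STEP 1) and at T2 (after the program), divided by the whole-cohort baseline SD.
2. Keep the Step 1-only and Steps 1 and 2 tables as pathway description, labelled as selected on T1 response, and state that neither their change from baseline nor their T1-to-T2 movement estimates the effect of a step. Effect sizes may stay in those tables if labelled this way.
3. State that the whole-cohort change is itself uncontrolled and does not separate program effect from natural recovery.

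The cost is a few sentences and one extra column per table. No new data are needed, and the stepping rule and participants' care are unchanged.

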- a) Retention (proportion of enrolled participants who completed follow-up assessments; proportion of participants who completed each module of step 1; proportion of participants who completed step 2 compared to the proportion of participants who consented to step 2)
- b) Adherence to step 1 and step 2 (percentage of sessions attended, reasons for not completing sessions, number of days overdue for completed questionnaires).
- c) The Intervention Appropriateness Measure (IAM). The IAM is a 4-item validated measure (Weiner et al., 2017) with items rated on a 5-point Likert scale from 'completely disagree' to 'completely agree' with higher scores indicating greater intervention appropriateness.

Intervention Feasibility

The feasibility of this intervention will be assessed using

- a. The Feasibility of Intervention Measure (FIM). The FIM is a 4-item validated measure (Weiner et al., 2017) with items rated on a 5-point Likert scale from 'completely disagree' to 'completely agree' with higher scores indicating greater intervention feasibility (Appendix A.4).
- b. Qualitative and quantitative feedback provided in study questionnaires completed after each chapter for STEP 1 and again at the end of STEP 2 of the program where applicable (T1Q-A and T2Q-A). Key indicators will include the number of chapters of the self-management booklet attempted / completed, completion of STEP 1 within 6 weeks and STEP 2 in 4 sessions. Additional details about barriers to completion will be sought.
- c. Qualitative field notes maintained by research team.

Intervention Acceptability

Intervention acceptability will be assessed using

- a. The Acceptability of Intervention Measure (AIM) will be used to measure acceptability (Appendix A.4). The AIM is a 4-item validated measure (Weiner et al., 2017) with items rated on a 5-point Likert scale from 'completely disagree' to 'completely agree' with higher scores indicating greater intervention acceptability. Intervention acceptability was also measured in the researcher-administered questionnaires (T1Q-A and T2Q-A) designed to elicit participants reports on aspects such as uptake of each module, time spent on each module, completion of module-based activities, perceived helpfulness of modules and barriers to reading modules and completing activities.

REFRESH: Finding New Energy after Cancer

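### The Step 1-only group is defined by participation, so it merges people who needed no step-up with people who were offered STEP 2 and did not take it, and its mean change moves with the refusal rate

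*Protocol*

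**What the plan says.** The Data Analysis section states that changes in FACIT-F, PSEFSM and EQ-5D-5L "will be analysed descriptively (means and standard deviations"). It fixes the grouping by participation: change is reported "separately for patients who participate in Step 1 only" and, as the second group, for those who take part in both steps. The effect size is "mean change divided by the baseline standard deviation".

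The section on the TIME 1 questionnaires sets the step rule. Participants who gain 10 or more FACIT-F points "will finish their CBT Fatigue treatment, unless they score below 34 (severe"). Those "less than 10 points higher than baseline and/or below 34 will be offered STEP 2", and the psychologist's judgement at the week 5 call also enters the decision. The same section covers follow-up of everyone who does not enter STEP 2, whatever the reason: "Participants who do not go on to STEP 2 of the program will complete Time 2 Part B Questionnaires (T2Q-B").

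Two other places show that entry to STEP 2 is voluntary. The description of the STEP 2 intervention speaks of people who meet the criteria and also agree to take part. Under Intervention Appropriateness, retention includes the "proportion of participants who completed step 2 compared to the proportion of participants who consented to step 2".

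Project Design and the STEP 1 procedures allow people who are struggling with the booklet at the week 2 call to be fast-tracked to STEP 2.

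**The concern.** The grouping follows what people took part in, not why they stopped or continued. Someone who gained at least 10 points and finished, and someone who gained little, was offered STEP 2 and declined, both took part in Step 1 only. Both are due the Time 2 form, so both contribute change scores under the same label. No passage separates them.

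The second group has a similar problem. It places people who may hardly have opened the booklet before being fast-tracked beside people stepped up after the full five weeks.

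The Evaluation section intends these outcomes as preliminary data for a later effectiveness study. A reader of the results is likely to take the Step 1-only figure as the course of people for whom self-management sufficed. As defined, that figure also reflects how acceptable STEP 2 was to those offered it.

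**Working it through.** **The protocol's own figure.** The STEP 2 intervention section expects about half to progress: 50 × 0.50 = 25 eligible, which reproduces the stated 25. The 53% given in the background for the earlier sleep programme would make it 26.5. The protocol turns a progression rate into a number eligible, so it treats eligibility and uptake as one quantity here, and it estimates no refusal rate.

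**Who is in each group**

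| Route | Group under Data Analysis |
|---|---|
| Gain of 10 or more, score not below 34, finished | Step 1 only |
| Gain below 10 and/or score below 34, offered STEP 2, declined or did not attend | Step 1 only |
| Gain below 10 and/or score below 34, entered STEP 2 | Steps 1 and 2 |
| Fast-tracked at week 2 | Steps 1 and 2 |

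Clinical judgement can move individuals between the first three rows.

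**Effect of merging on the Step 1-only mean at Time 1.** Take 25 who finish and 25 eligible for STEP 2, and let d be the share of the eligible who decline. Then

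mean = (25 × m_finished + 25d × m_declined) / (25 + 25d).

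Both mean gains and d are assumptions.

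| d | Decliners in group | Gains 14 and 1 | Gains 12 and 0 |
|---|---|---|---|
| 0% | 0 of 25 | 14.0 | 12.0 |
| 20% | 5 of 30 (17%) | (350 + 5)/30 = 11.8 | 300/30 = 10.0 |
| 40% | 10 of 35 (29%) | (350 + 10)/35 = 10.3 | 300/35 = 8.6 |

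The last entry is below the 10-point change that the protocol calls clinically significant, although under the score rule everyone who finished gained at least 10 at Time 1.

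**What does not move.** The Time 1 change over all participants precedes any refusal. If all eligible people have the mean gain assumed for decliners, it is (25 × 14 + 25 × 1)/50 = 7.5 in the first set and (25 × 12 + 25 × 0)/50 = 6.0 in the second, at every d.

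**Effect size.** The mixed mean is the numerator, so the effect size shifts in proportion for a given baseline SD. The section does not say whether that SD is the group's or the whole sample's.

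**The case against.** The strongest reply is that little hangs on this. The study is a feasibility study. The Evaluation section puts implementation first and treats outcome change as exploratory, and Aim 1d looks to the proportion referred to STEP 2. Consent to STEP 2, withdrawals with reasons, and deviations from the stepped-care protocol are all recorded. Given the ns, the two Time 1 group means also recombine to the overall Time 1 change. All of this stands, and it limits the weight of the point. It does not remove it, because change scores by pathway are still not planned and the label invites misreading.

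Four stronger readings are tempting but not supported:

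- *Refusal alone could pull the mean from 11.8 to 7.7.* A reader might infer this by comparing 25 eligible with 20% declining against 35 eligible with 40% declining, where (15 × 14 + 14 × 1)/29 = 7.7. The number who finish has changed as well: the whole-sample Time 1 change is 7.5 in the first case and (15 × 14 + 35 × 1)/50 = 4.9 in the second. With eligibility fixed, going from 20% to 40% refusal moves the mean from 11.8 to 10.3, about 1.5 points.
- *All decliners are non-improvers.* Someone who starts below 24 can gain 10 points, still score below 34, and be offered STEP 2. A mean gain near zero for decliners is an assumption towards the unfavourable end.
- *People with no Time 1 form dilute the Time 1 mean.* Missing forms are not imputed, so these people have no Time 1 change score. They could enter only through a later Time 2 form.
- *The Step 1-only result is the protocol's test of whether self-management is enough.* The protocol does not claim this.

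**Conclusion.** The point holds as a problem of definition. The stated grouping merges people who finished because no step-up was indicated with people who were offered STEP 2 and did not take it. It also merges early fast-tracked participants with those stepped up after STEP 1. The Step 1-only mean and effect size therefore depend on STEP 2 refusal.

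With 25 of 50 eligible and the two sets of assumed gains above, the mean falls by 2.0 to 2.2 points at 20% refusal and by 3.4 to 3.7 points at 40%. These sizes rest wholly on assumed gains and refusal rates. The shift in this group is zero if nobody declines and the score rule is applied strictly. No test or error rate is involved. The change is worth making because it is cheap and these figures are meant to inform a later study.

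**What to change.** Amend the grouping sentence in Data Analysis:

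1. Report the Time 1 change for all participants with a Time 1 form as the summary of STEP 1. The group that finished is largely selected on its own Time 1 gain, so its mean cannot serve that purpose.
2. Report change by step decision and uptake, with n for each: finished after STEP 1 with no step-up indicated; stepped up at Time 1 and attended at least one session; offered STEP 2 but declined or did not attend; fast-tracked before Time 1. For people with no Time 1 form, give the count only.
3. Standardise every effect size by the whole-sample baseline SD. Where a cell is very small, give only n and raw change.

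The cost is a wording change and one derived variable, built from Time 1 scores, the recruitment spreadsheet and the stepped-care notes already kept. No assessment is added and care is unchanged. The drawback is small cells: at 20% refusal the declined group would have about 5 people. That is tolerable in descriptive output, and the planned two-group table can be shown alongside.
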